**Table 2- Projected Enrollment is Shown Below According the Study Site**

| Site   | UCLA | UCSD | UCI | UC Davis |  |  | Total |
|--------|------|------|-----|----------|--|--|-------|
| Kidney | 130  | 20   | 30  | 20       |  |  | 200   |

**Table 3 - Adult Transplant Subjects – Trough Levels:**

\*Based on individual subject therapeutic level.

|                        |  | 1 mo. | 2mo. | 3mo. | 6mo. | 9mo. | 12mo. |
|------------------------|--|-------|------|------|------|------|-------|
| UCLA/UCSD/UCI/UC DAVIS |  | 8-11  | 8-11 | 8-11 | 4-11 | 4-11 | 4-11  |

The tacrolimus level ranges listed in Table 3 are target ranges. The adjustment of trough level should be based on the clinical judgment of the Principal Investigator and the subject's primary physician. The product insert recommends a trough level of 4-11. If the trough level falls outside the 4-11 range the Investigator must provide a justification. Trough levels will be monitored

throughout the study. For more details see Table 5 Study Schedule. All adjustments will be recorded in the subject's study file.

### **6.2.8 Study regimens:**

Eligible and consented subjects will be randomized into the 2 groups below:

Arm 1 (n=40) will receive brand tacrolimus for the entire study

Arm 2 (n=160) will receive generic tacrolimus for the entire study

According to their standard practice and attending physician and surgeon recommendation, subjects should also be on a maintenance regimen consisting of any of the following medications: mycophenolate mofetil, mycophenolate sodium, corticosteroids, azathioprine. Concomitant belatacept administration is not permitted. To minimize confounding factors, efforts will be made between UCSD, UCI, UC Davis, and UCLA to synchronize a similar organ specific maintenance immunosuppressive regimen across the four sites. However, each subject's maintenance regimen will ultimately be at the discretion of the treating physician. The tacrolimus level will be maintained between 4-11 ng/dL during the duration of the study.

### **6.2.9 Study Visits and Post randomization follow-up**

A total of 7 visits, over a 12-month period, are planned as follows. All subjects will continue to receive routine labs as part of their standard of care from their treating physician. For detailed information about the study labs schedule see Table 5 Study Schedule. Safety labs are done as part of their standard of care from their treating physician.

Subjects on Phase 1 who need more study drug medication before his or her next study visit, will receive a new supply from clinic. Subjects on Phase 2 will receive drug from their pharmacy/hospital.

**First (Baseline) Visit** (up to 14 days after transplant but before the study subject is discharged from the hospital):

- Subject reviews and signs consent form
- Review of subject's medical history
- Review of subject's current medications
- Review of subject's physical exam including vital signs (blood pressure, temperature, pulse and respiration rate), height and weight
- Review of clinical labs
- Randomization of subject in Phase 1 only
- Subject will receive drug at discharge.

#### **Month 1 Visit:**

- Review of subject's current medications
- Review of subject's physical exam including vital signs (blood pressure, temperature, pulse and respiration rate), height and weight
- Review of any changes in subject's health and any reactions to the study medication will be recorded
- Review of routine standard of care clinical labs

- Subject returns completed dosing diary and receives new dosing diary
- Subject will receive drug if applicable

**Month 2/3 Visit:**

- Review of subject's current medications
- Review of subject's physical exam including vital signs (blood pressure, temperature, pulse and respiration rate), height and weight
- Review of any changes in subject's health and any reactions to the study medication will be recorded
- Subject returns completed dosing diary and receives unfilled dosing diary
- Subject will receive drug if applicable

**Month 6/9/Visit:**

- Review of subject's current medications
- Review of subject's physical exam including vital signs (blood pressure, temperature, pulse and respiration rate), height and weight
- Review of any changes in subject's health and any reactions to the study medication will be recorded
- Review of routine standard of care clinical labs
- Subject returns completed dosing diary and receives unfilled dosing diary
- Subject will receive drug if applicable.

**Month 12 Visit (End of Study Visit):**

- Review of subject's current medications
- Review of any changes in subject's health and any reactions to the study medication will be recorded
- Review of routine standard of care clinical labs
- Subject returns final completed dosing diary
- Subject returns any drug remaining in his or her possession to the study team if applicable (Phase 1 only).

A safety follow-up phone call will be made at month 13 (+/- 1 week) to record patient's wellbeing and graft survival. This call will serve as the last AE follow-up if any was reported at month 12.

**Routine Standard of Care Clinical Labs**

All subjects will continue to have routine blood and urine collection to monitor kidney function as part of their standard of care treatment at UCLA or UCSD, UCI, and UC Davis. These routine blood collections are not included in the total blood for the study discussed above. The schedule for these routine blood and urine collections will depend on the subject's condition and will be at their treating physician's discretion.

**6.3 Adherence**

Adherence will be measured with daily medication diaries, and with the coefficient of variation of tacrolimus in subjects' blood.

## 6.4 Blinding/Unblinding

As this is an open label study, no arrangements need to be made for blinding or potential unblinding.

## 6.5 Prohibited and Restricted Therapies During the Study

Use of experimental drugs and the immunosuppressive medication belatacept are prohibited for study participants.

### DRUG INTERACTIONS

- Mycophenolic Acid Products: Can increase MPA exposure after crossover from cyclosporine to Prograf; monitor for MPA-related adverse reactions and adjust MMF or MPA-dose as needed
- Nelfinavir and Grapefruit Juice: Increased tacrolimus concentrations via CYP3A inhibition; avoid concomitant use
- CYP3A Inhibitors: Increased tacrolimus concentrations; monitor concentrations and adjust tacrolimus dose as needed with concomitant use as per routine clinical care.
- CYP3A4 Inducers: Decreased tacrolimus concentrations; monitor concentrations and adjust tacrolimus dose as needed with concomitant use as per routine clinical care.

### Limitations of Use:

- Do not use simultaneously with cyclosporine
- Intravenous use reserved for subjects who cannot tolerate capsules orally
- Use with sirolimus in kidney transplant has not been established

### CONTRAINDICATIONS

- Hypersensitivity to tacrolimus or HCO-60 (polyoxyl 60 hydrogenated castor oil)

## 6.6 Non-therapy Precautions and Restrictions

Subjects should not eat grapefruit or drink grapefruit juice in combination with Prograf or generic tacrolimus. Subjects will be instructed to avoid eating grapefruit and drinking grapefruit juice during the study.

## 6.7 Withdrawal of Subjects from Study

All efforts should be made to follow all subjects for the entire duration of the study.

Withdrawal of a subject from study medication does not imply that the subject is withdrawn from the study. Subjects MUST be discontinued from study therapy AND withdrawn from the study for the following reasons:

- Withdrawal of informed consent (subject's decision to withdraw for any reason)
- Any clinical AE, laboratory abnormality, or intercurrent illness which, in the opinion of the investigator, indicates that continued treatment with study therapy and further participation in the study (including obtaining vital status of the subject and allograft) is not in the best interest of the subject.
- If the subject's physician switches them from tacrolimus to another immunosuppressant medication for their safety
- Termination of the study
- Subjects who become prisoners or become involuntary incarcerated for treatment of either a psychiatric or physical (e.g., infectious disease) illness.

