Statistical methods: The primary efficacy endpoint will be analyzed as time-to-event, with follow-up time measured in days from the date of transplant to the date of composite endpoint. Statistical testing of time until composite event will be done for the intention-to-treat population, with adjustment for center (Cox regression). Data will also be collected on subjects who are lost to follow up. The intention-to-treat population will consist of all randomized patients who received at least 1 dose of investigational drug (brand or generic tacrolimus).

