### 3.4 Sample Size Determination

The total number of subjects (200) is based on statistical calculation to have more than 80% power to detect a non-inferiority margin of 26 percentage points of the composite endpoint of acute rejection, graft loss and death over the baseline of 13% in the brand tacrolimus at one year post-transplantation. (See details in next paragraph.)

For power considerations regarding the primary objective, the following assumptions are made:

1. Subjects will be uniformly enrolled over 1-year accrual period
2. Primary analysis will be done via non-inferiority, log-rank tests on an intention-to-treat basis comparing generic recipients (Arm 2) with brand recipients (Arm 1)
3. Data will be also collected from standard-of-care records on subjects who are lost to follow-up
4. Overall, 13% of subjects are expected to experience the primary endpoint by 1 year post-transplant, yielding a yearly hazard rate for the reference group of  $-\log(0.87) = 0.14$

Given these assumptions, 200 subjects (if 50 and 150 in brand and generic groups, respectively) are needed to observe 25 events (6 and 19 in brand and generic groups, respectively). These numbers achieve >80% power at a 0.05 significance level to detect a non-inferiority hazard ratio of 3.54 when the actual hazard ratio is 1.0. PASS statistical software (version 13.0) was used for calculation. For completeness, we acknowledge that the study has 80% power only for the specific set of conditions listed above and may lack canonical power when analyzing hypotheses involving secondary endpoints.

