**Table 1 - Via PASS**

Power  $\geq$  80% (alpha = 0.05, 5% dropout, 12 mo. study time)

| Scenario | Sample Size (N) | Brand Surv% (Haz rate/mo) | Equiv HR | Generic Non-inferior Surv% (hrate/mo) | 1-year Margin of inferiority |
|----------|-----------------|---------------------------|----------|---------------------------------------|------------------------------|
|          |                 |                           |          |                                       |                              |

|             |     |              |      |              |                   |
|-------------|-----|--------------|------|--------------|-------------------|
| Kidney only | 200 | 87% (0.0116) | 3.54 | 61% (0.0411) | $\Delta=26\%$ pts |
|-------------|-----|--------------|------|--------------|-------------------|

Source: PASS 13 Power Analysis and Sample Size Software (2014). NCSS, LLC. Kaysville, Utah, USA, [ncss.com/software/pass](http://ncss.com/software/pass). (Non-inferiority logrank test.)

A descriptive analysis will be incorporated of generic supplied within the analysis.

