## EARLY WITHDRAWAL:

Subject participation in this study will last for approximately 1 year. If the subject withdraws at any time early from the study, for any reason, the subject will be interviewed 30 days after leaving the study to check on how the subject is doing after coming off the study drug. This follow-up is to evaluate their safety.

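### Section 6.7 requires subjects switched off tacrolimus for safety to leave the study, which conflicts with the one-year follow-up and intention-to-treat analysis; minor in size and cheap to fix.

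*Combined protocol and SAP*

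**What the plan says.** Section 6.7 opens with two general statements: "All efforts should be made to follow all subjects for the entire duration of the study", and "Withdrawal of a subject from study medication does not imply that the subject is withdrawn from the study". It then sets out exceptions: "Subjects MUST be discontinued from study therapy AND withdrawn from the study for the following reasons". One of these applies when the subject's "physician switches them from tacrolimus to another immunosuppressant medication for their safety". The list is not limited to Phase 1.

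For anyone who leaves early, the Early Withdrawal paragraph specifies one contact: "the subject will be interviewed 30 days after leaving the study". Its stated purpose is safety.

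Other sections point towards complete one-year ascertainment:

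- **6.2.5** says that every subject is to be followed for a year after transplant.
- **4.2** puts the primary test on the intention-to-treat population.
- **Synopsis (Statistical methods)** says "Data will also be collected on subjects who are lost to follow up".
- **3.4** lists among its power assumptions "Data will be also collected from standard-of-care records on subjects who are lost to follow-up".
- **4.1** covers all enrolled subjects and draws on routine care, but its data sets are updated at study visits.

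Section 4.2 has no counting or censoring rule for a subject withdrawn under 6.7.

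**The concern.** The primary endpoint is the time to the first of rejection, graft failure or death. A subject taken off tacrolimus for safety before any of these remains at risk, perhaps at raised risk. An intention-to-treat analysis needs that subject's later outcome. Section 6.7 instead ends participation automatically, and no other section clearly restores the follow-up.

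If such subjects were in practice censored at the switch, the censoring could be informative. Losing more generic than brand events would favour a finding of non-inferiority, and losing more brand events would count against it. Only about 5 brand events are expected, so the result is sensitive to one or two of them. The study is open label (6.4), so the physician deciding on a switch can know the product.

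**Working it through.** **1. The plan's own figure.** Section 3.4 gives 6 brand and 19 generic events, a margin of 3.54 and power above 80%; 4.2 makes the test one-sided at 5%.

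- SE = sqrt(1/6 + 1/19) = 0.468
- Power = Φ(ln 3.54 / 0.468 − 1.645) = Φ(1.05) = 0.854, which agrees with the plan.

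The checks below use the allocation in 6.2.4 and 6.2.8, 40 brand and 160 generic, and assume that all 200 subjects are analysed. At 13% this gives 40 × 0.13 = 5.2 and 160 × 0.13 = 20.8 expected events.

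**2. Which events are exposed.** Only a switch before any primary event, followed by a first event within the year, can lose information. If rejection or graft failure prompted the switch, the primary event has normally been counted already. Dose changes and brand-generic changes do not trigger the rule, because the subject stays on tacrolimus.

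**3. Modelling the switch directly.** Assumptions:

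- brand hazard −ln(0.87) = 0.139 per year, with one year of follow-up
- switch times uniform over the year and unrelated to earlier prognosis
- hazard three times higher after the switch
- unadjusted Cox model; non-inferior if the 90% upper bound is below 3.54
- 8,000 simulated trials per case

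| Hazard ratio before switch | Switching, brand / generic | Declared non-inferior, censored at switch | Declared non-inferior, all events counted |
|---|---|---|---|
| 1.0 | 5% / 5% | 72.7% | 74.8% |
| 1.0 | 10% / 10% | 71.8% | 75.9% |
| 1.0 | 10% / 5% | 72.1% | 77.9% |
| 3.54 | 5% / 5% | 5.8% | 6.0% |
| 3.54 | 5% / 15% | 5.8% | 4.6% |

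Power losses: 74.8 − 72.7 = 2.1, 75.9 − 71.8 = 4.1 and 77.9 − 72.1 = 5.8 points. Simulation error is about sqrt(0.73 × 0.27 / 8000) = 0.5 points for power. With no switching the simulated power is already about 73%, so that level is not caused by 6.7.

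**4. The plan's only attrition figure.** Table 1 is headed ("alpha = 0.05, 5% dropout, 12 mo. study time"). Five per cent is 2 of 40 brand and 8 of 160 generic subjects. Take the extreme case in which all ten would have had an event, starting from 5 and 21:

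- 3 versus 13 events remain
- HR = ln(1 − 13/160) / ln(1 − 3/40) = 1.09
- SE = sqrt(1/3 + 1/13) = 0.641
- Upper bound = 1.09 × exp(1.645 × 0.641) = 3.12, which still passes.

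**5. What a changed conclusion would need.** By the same formulas, 5 versus 21 events gives an upper bound of 2.39. Losing one brand event and no generic event gives 3.28 (passes); losing two gives 4.98 (fails).

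For a subject event-free at an assumed month-6 switch, the chance of an event in the remaining half-year is 1 − exp(−3 × 0.139 × 0.5) = 0.188 at threefold hazard, or 0.067 at baseline hazard. Losing two brand events in expectation therefore needs 2 / 0.188, about 11 of 40 brand subjects switching, or 2 / 0.067, about 30 of 40, with no generic loss.

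If 20% of generic and 10% of brand would-be events were removed at a hazard ratio of 3.54, the simulated false-positive rate would be 9.3%, against 5.9% with no loss. Expected generic events there are 160 × (1 − 0.87^3.54) = 62, so 20% is about 12. That needs about 24 generic switches (15%) at threefold hazard, since 12.4 / 0.522 = 23.8. At baseline hazard it needs about 57 (36%), since 12.4 / 0.218 = 56.9. Every loss would also have to fall on a subject who would otherwise have had a counted event.

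**The case against.** The strongest defence is that the plan intends full ascertainment. Section 6.2.5 follows everyone for a year, 6.7 asks for all efforts, 4.1 builds its data from routine care, and 3.4 uses standard-of-care records. Lost to follow-up is not defined, and a transplant recipient on a different drug presumably stays in care. A site could treat a withdrawn subject as lost to follow-up and capture the later events.

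This stands as far as intent goes. A reader might infer from 6.7 that later events will be discarded, or that subjects will be censored at the switch. The documents say neither. What remains is a conflict between a specific mandatory rule and several general statements, and the text does not say which prevails.

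A second objection is that the endpoint counts first events only, so the switches most closely tied to rejection usually follow an event already recorded. This also stands, and it is a main reason why the effect is small.

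A third is that other routes out of the study exist: discretionary withdrawal for non-compliance (7.3) and the adverse-event reason in 6.7. The first belongs in the same fix. The second rests on an investigator's judgement that further participation, even establishing vital and graft status, is not in the subject's interest; the switch rule asks for no such judgement.

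**Conclusion.** The conflict is real: 6.7 mandates an exit that 6.2.5, the follow-up sentence in 6.7 and the intention-to-treat analysis in 4.2 do not allow for. First events after a safety switch are not assured of being counted.

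The likely size is small. At assumed switch rates of 5 to 15% with a threefold later hazard, censoring at the switch costs about 2 to 6 points of power at a true hazard ratio of 1.0 and leaves the false-positive rate near 5 to 6%. This rests on assumed rates, on all 200 subjects being analysed as 40 and 160, and on switching being unrelated to prognosis before the switch. Switches aimed at subjects about to have an event would be more informative than modelled.

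A reader might go further and infer that the rule could reverse the conclusion or materially inflate the false-positive rate. That would need high or strongly unequal loss. Open-label treatment makes unequal loss possible, but the documents do not show it. The point is a cheap improvement of minor severity.

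**What to change.** - **6.7 and the Early Withdrawal paragraph:** take the physician switch off the list of mandatory reasons for leaving, so that it stops study drug only. Unless the subject withdraws consent to record access, collect rejection, graft status and vital status from standard-of-care records to 12 months.
- **7.3 (Compliance):** apply the same record-based collection to subjects withdrawn for non-compliance.
- **4.2:** state that these events count in the primary analysis whatever drug the subject is then taking, and that subjects who withdraw consent are censored at withdrawal.

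The cost is an IRB-approved wording change and a little extra record review. The record source is already used in 3.4, and 7.3 already provides a form for access to medical records. No extra subjects or visits are needed. Subjects already withdrawn may need to give renewed permission.

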## EARLY WITHDRAWAL:

Subject participation in this study will last for approximately 1 year. If the subject withdraws at any time early from the study, for any reason, the subject will be interviewed 30 days after leaving the study to check on how the subject is doing after coming off the study drug. This follow-up is to evaluate their safety.

## 7.0 STUDY PROCEDURES AND OBSERVATION

### 7.1 Time and Events Schedule

The following windows are permitted for subsequent doses:

| Visit       | Visit Window             |
|-------------|--------------------------|
| Month 1-3   | Target date $\pm$ 3 days |
| Month 6 -12 | Target date $\pm$ 7 days |

### 7.2 Study Visits

#### Baseline Visit

At the baseline visit, 2-14 days after transplantation, subjects will undergo screening for eligibility by review of inclusion and exclusion factors and informed consent as administered by study personnel. Subjects will be consented in the privacy of their own rooms. The PI will review the informed consent with the patients and the subjects will have ample time to ask questions. Once the subject has signed the consent form then they will be given a copy of the signed consent form. After subjects have been consented, the following steps will be taken: Randomization to Arm 1 or 2 (for Phase 1 only), review of medical history and concomitant medications, review of labs, vital sign evaluation, and physical examination. Subjects will receive a study diary to record the name of the drug, dates, and times of taking tacrolimus (see Appendix 2 for Subject Diary).

#### Visits 1,2,3,6,9, and 12

At each additional study visit (Month 1, 2, 3, 6, 9, and 12 (End of Study Visit), (see Schedule of Events below), subjects will undergo a review of medical history and concomitant medications, review of labs, vital sign evaluation and physical examination. For more details see Table 5 Study Schedule. At the 12-month visit, subjects will return the study diary, any remaining study drug, and any related study materials. The study dosing diary will be reviewed at each study visit when available.

Trough levels will be monitored throughout the study (see Table 3 for Trough Level schedule). Subjects will continue to have routine blood and urine collection to monitor kidney function as part of their standard of care treatment at UCLA, UCSD, UCI, or UC Davis. The results of a few of these labs will be collected as part of study safety labs. For more details see Appendix 1.

### Table 5 - Study Schedule

|   | Baseline | 1 mo. | 2 mo. | 3 mo. | 6 mo. | 9 mo. | 12 mo. |
|---|----------|-------|-------|-------|-------|-------|--------|
| Obtain informed consent                     | x        |       |       |       |       |       |        |
| Confirm inclusion/exclusion                 | x        |       |       |       |       |       |        |
| Review medical history                      | x        | x     | x     | x     | x     | x     | x      |
| Review physical exam                        | x        | x     | x     | x     | x     | x     | x      |
| Review concomitant medications              | x        | x     | x     | x     | x     | x     | x      |
| AE monitoring (Safety labs)                 |          | x     | x     | x     | x     | x     | x      |
| Review of labs                              | x        | x     | x     | x     | x     | x     | x      |
| Randomization *                             | x        |       |       |       |       |       |        |
| Tacrolimus dispensation (if applicable)     | x        | x     | x     | x     | x     | x     |        |
| Tacrolimus level from routine clinical labs |          | x     | x     | x     | x     | x     | x      |
| Review dosing diary                         |          | x     | x     | x     | x     | x     | x      |

\*Randomization for Phase 1 only, no randomization will occur during Phase 2 as all subjects will be placed on generic drug.

